3.2. Exclusion Criteria

- 3.2.1. Patients receiving any other investigational agents
- 3.2.2. Patients who are pregnant or breast-feeding
- 3.2.3. Patients with clinically significant heart disease (NYHA Class III or IV)
- 3.2.4. Known or suspected hypersensitivity to azacitidine or mannitol.
- 3.2.5. Patients with advanced malignant hepatic tumors.

4. Treatment Plan

4.1. **TKI:** Patients will continue receiving TKI at the dose they had been receiving during the last 6 months.

4.2. **AZA:**

Phase I: patients will be treated in cohorts of 3. The starting dose will be dose level 0 (50 mg/m²/d x 3 days subcutaneous or intravenous; Table 1).

4.2.1. At least 3 patients will be entered at each level. All patients treated at any one dose level must have been observed for at least four weeks before escalating to the next dose level. Patients who come off study prior to the first four weeks and have not experienced a DLT will be replaced.

Table 1: Dose escalation levels	
Dose level	AZA (mg/m ² /d x 3 days)
-3	25 (1 day only)
-2	25 (2 days only)
-1	25
0	50
1 (Target dose)	75
2	75 (for 5 days)
3	75 (for 7 days)

4.2.2. Dose escalation will be done as follows:

Dose-limiting toxicity in	Result
0/3	Escalate to next level
1/3	Enter 3 more patients
≥2/3 or ≥ 2/6	MTD exceeded. This dose level will be declared the maximally administered dose. Expand previous level to include a total of 6 patients if not already accrued to this number.

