e-mail: [contact]

9. Statistical Considerations

9.1. This is a single arm, open label, phase I-II trial to evaluate the toxicity and efficacy of the combination of AZA and a TKI in CML patients in complete cytogenetic remission with minimal residual disease. A total of 48 patients will be accrued at a rate of 1 to 2 patients per month.

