9.2.1.1. Three patients will be enrolled at the starting dose level

9.2.1.2. If 0/3 patient experiences DLT at a given level, enroll three patients to the next higher dose level

9.2.1.3. If 1/3 patient experiences DLT at a given level, enroll additional three patients to the same dose level

9.2.1.4. If 2/3 or 2/6 patients experience DLT at a given level, the MTD has been exceeded and dose escalation will be stopped. Up to three additional patients will be enrolled at the next lower dose level if only 3 patients were treated at that level.

9.2.2. MTD is defined as the highest dose level in which 6 patients have been treated and one or fewer patient experiences DLT.

The MTD identified in phase I part will be recommended for phase II. If MTD is not determined, the highest AZA level of 75 mg/m²/d x 3 days will be used as the recommended phase II dose.

A maximum of 18 patients will be accrued for phase I part. The data from the 6 patients treated at the recommended phase II dose level (MTD or 75 mg/m²/d x 3 days if MTD is not determined) will be used in phase II part.

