9.3. Phase II

The primary endpoint for phase II portion is the decrease of transcript levels by at least one log (or undetectable transcript level) within 12 months. Including the 6 patients treated at the recommended phase II dose level in the phase I part, a total of 36 patients will be accrued.

9.3.1. **Efficacy Monitoring**

Since the efficacy of the drug will be assessed over a long period of time (12 months) and the accrual rate is relatively fast (1-2 patients per month), no formal futility monitoring rule will be applied. However, the PI and the study committee will meet regularly, and the study will be stopped early if consensus has been reached on any clear indications of poor efficacy of the drug.

9.3.2. **Toxicity Monitoring**

The method of Thall, Simon, and Estey will be used to perform interim safety monitoring [1]. The safety monitoring of the trial will be initiated after the first 6 patients have been evaluated, and then monitored continuously. The monitoring rule for toxicity is $P(\theta_E > 0.20 | \text{data}) > 0.90$, where θ_E is the proportion of any DLT (as defined in section 4.3.3), and is assumed to follow a non-informative prior of Beta (0.4, 1.6). Namely, the trial will be terminated if at any time during the study there is a more than 90% chance that the average rate of DLT is more than 20%. The stopping boundaries of the trial are ≥ 3 out of 6, ≥ 4 out of 7, ≥ 5 out of 10, ≥ 6 out of 14, ≥ 7 out of 18, ≥ 8 out of 22, ≥ 9 out of 26, ≥ 10 out of 30, ≥ 11 out of 34 patients experienced DLT.

Table 2: Operating characteristics of Safety Monitoring (based on 10000 simulations)				
True Probability	Stop Probability	Trial Sample Size Percentile		
		25%	50%	75%
0.10	0.02	36	36	36
0.20	0.25	36	36	36
0.30	0.69	6	17	36
0.40	0.96	6	8	16

All calculations were performed using Multc99.

9.4. **Statistical Methods**

Data analysis will be performed using SAS or S-plus, whichever is appropriate. All patients who receive at least one dose of therapy will be included in the primary efficacy and toxicity analysis. Patients who do not have molecular response and

withdraw within 12-months after initiation of treatment will be counted as failure in the primary efficacy analysis.

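### Sections 9.2.2 and 9.3 count six phase I patients at the recommended dose, but after 0 of 3 DLTs at level 1 the steps in 9.2.1 leave only three there

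*Combined protocol and SAP*

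**What the plan says.** **The count.** Section 9.2.2 says that "The data from the 6 patients treated at the recommended phase II dose level" will be used in phase II. Its parenthesis names two cases: the dose is the MTD, or it is 75 mg/m²/d x 3 days because no MTD was determined. Section 9.3 repeats the number: "Including the 6 patients treated at the recommended phase II dose level in the phase I part, a total of 36 patients will be accrued". Section 9.2.2 adds "A maximum of 18 patients will be accrued for phase I part", and section 9.1 says "A total of 48 patients will be accrued".

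**The steps in 9.2.1.**
- After no DLT in three: "If 0/3 patient experiences DLT at a given level, enroll three patients to the next higher dose level".
- After one DLT in three: "If 1/3 patient experiences DLT at a given level, enroll additional three patients to the same dose level".
- After two DLTs, the MTD is exceeded and "Up to three additional patients will be enrolled at the next lower dose level if only 3 patients were treated at that level".

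The dose table in 9.2 stops at level 1 (75 mg/m²/d x 3 days), which 9.2.2 also treats as the highest level. The MTD definition in 9.2.2 requires six treated patients with at most one DLT.

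**Section 4.** Section 4.2.1 sets a minimum of three patients per level. Once a level has exceeded the MTD, section 4.2.2 says "Expand previous level to include a total of 6 patients if not already accrued to this number". Table 1 lists levels 2 and 3 above level 1. Section 4.3 nevertheless sets the phase II dose at 75 mg/m² for 3 days unless the MTD is lower.

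**The concern.** The count and the steps do not agree. Under 9.2.1 a level reaches six patients by one of two routes: one DLT among its first three, or a later finding that the level above is too toxic. A level 1 cohort with no DLT in three takes neither route. The instruction is to move up, and 9.2 has nothing to move up to.

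That is also the path on which 75 mg/m²/d x 3 days goes forward without having met the MTD definition. If six had been treated there with at most one DLT, level 1 would be the MTD; with two or more it would be exceeded. So 9.2.2 expects six patients in the very case where the steps deliver three.

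Two things are at stake. The number of phase I patients counted in phase II, and so the number of new patients needed, is not settled by the text. In addition, the phase I objective of determining an MTD is not met at the dose taken forward, which rests on DLT data from three patients.

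**Working it through.** **1. The plan's own figures.** Three levels of six give 3 × 6 = 18, the phase I maximum. The overall total is 18 + 36 − 6 = 48, as stated. For power, section 9.4 gives a null response rate of 5%, an alternative of 20% and a one-sided α of 5%. With n = 36 the smallest exact critical value is 5 responses: P(X ≥ 5 | 36, 0.05) = 0.032, whereas 4 responses would give 0.104. Power is P(X ≥ 5 | 36, 0.20) = 0.873, matching the stated 87%. All these figures are consistent with six carried over.

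**2. Patients at level 1 under 9.2.1, once it is reached.**

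| Result at level 1 | Next step | Treated at level 1 |
|---|---|---|
| 0 of 3 | next level; none in 9.2 | 3 |
| 1 of 3, then 0 of 3 | meets the MTD definition | 6 |
| 2 or more DLTs | MTD exceeded; level 0 goes to six | level 1 not taken forward |

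**3. How often the first row occurs.** The documents give no DLT rates, so 5% to 30% is an assumed range. With true rate p and q = 1 − p, P(0 of 3) = q³ and P(1 of 3) = 3pq².

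| p | P(0 of 3) | P(1 of 3) |
|---|---|---|
| 5% | 0.857 | 0.135 |
| 10% | 0.729 | 0.243 |
| 20% | 0.512 | 0.384 |
| 25% | 0.422 | 0.422 |
| 30% | 0.343 | 0.441 |

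Since q³ > 3pq² when q > 3p, 0 of 3 is the likeliest first-cohort result for p below 25%. That range includes the 20% limit used in 9.3.2.

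These values are conditional on reaching level 1. For the whole trial, multiply by the chance of passing level 0, q₀³ + 3p₀q₀⁵:
- rates 5% and 10% at levels 0 and 1: 0.973 × 0.729 = 0.71
- rates 10% and 20%: 0.906 × 0.512 = 0.46
- rates 20% and 20%: 0.709 × 0.512 = 0.36

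**4. What three further patients could show.** Given 0 of 3, P(at least 2 DLTs in three more) = 3p²q + p³, which is 0.028, 0.104 and 0.216 at p = 10%, 20% and 30%. Multiplied by q³, the joint probabilities are 0.020, 0.053 and 0.074.

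**5. Effect on accrual.** With six carried over, 36 − 6 = 30 new patients are needed; with three, 36 − 3 = 33. If 0 of 3 occurs at level 1, phase I has used 3 + 3 = 6 patients, or 6 + 3 = 9 if level 0 needed six. The trial total is then 39 or 42, inside 48, and power stays at 87.3%.

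**6. A further ambiguity.** If level 0 had six patients with one DLT and level 1 then showed 0 of 3, the highest level meeting the six-patient definition is, read literally, level 0. The text does not say whether the definition or the fallback governs in that branch.

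**7. Section 4.** The minimum in 4.2.1 permits six but does not require them. The expansion in 4.2.2 needs a higher level to have failed. Under Table 1, 0 of 3 at level 1 leads to level 2, and level 1 reaches six only if level 2 exceeds the MTD. If levels 2 and 3 are tolerated, level 1 still holds three, and 4.3 still names that dose for phase II.

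**The case against.** The strongest reply is that six is plainly what the authors meant and the step list merely omits a line. The parenthesis in 9.2.2 names the undetermined-MTD case, the MTD definition needs six, the cap of 18 is three levels of six, and 4.2.1 allows more than three. This stands as evidence of intent, and for that reason the point is an inconsistency rather than a wrong calculation. It does not supply the missing step: a site following 9.2.1 as written would stop at three.

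Three stronger inferences are tempting, and the documents do not support them.

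- **That phase II loses power.** With three carried over and exactly 30 new patients, n = 33 and exact power is 0.818 (at least 5 responses, α = 0.023). But 9.3 fixes the total at 36, and 30 new patients is a subtraction, not a stated figure. The loss occurs only if the stated total is not met.
- **That opening phase II breaches the four-week observation rule.** In 4.2.1 that rule governs escalation to the next level, not the opening of phase II.
- **That toxicity at this dose would go unwatched.** Section 9.3.2 monitors DLTs continuously once six patients have been evaluated, with stopping at 3 or more of 6. What remains is narrower: if the carried-over patients count towards that six, three of them would be new phase II patients rather than all six coming from phase I.

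**Conclusion.** The inconsistency is real and does not depend on any assumed rate: the steps give three patients at level 1 after 0 of 3, while 9.2.2 and 9.3 count six. How often it matters does depend on assumptions. Given that level 1 is reached, the probability is 86%, 73%, 51% and 34% at true DLT rates of 5%, 10%, 20% and 30%. It is not the likeliest first-cohort result at 25% or above, and the whole-trial chance is lower, from 0.71 down to 0.36 in the scenarios shown.

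The main consequence is for the evidence behind the dose. Given 0 of 3, three more patients would show two or more DLTs with probability 3%, 10% and 22% at rates of 10%, 20% and 30% (jointly 2%, 5% and 7%). The efficacy analysis is unaffected while the total of 36 is kept. This is a minor point, worth correcting because it leaves a stated count and the phase I objective unmet on a common path.

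**What to change.** Reconcile 9.2.1, 9.2.2, 9.3 and the 9.2 dose table with 4.2.1, 4.2.2, 4.3 and Table 1, so that the cohort steps and the stated six patients agree. The reconciled text should make clear:

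- which level is the highest in phase I, since Table 1 lists levels 2 and 3 and the 9.2 table does not;
- how many patients are treated at the dose taken forward when no MTD is determined;
- whether the MTD definition or the fallback applies when level 0 has six patients and level 1 has three.

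If three remains possible, state the carry-over as 3 or 6 and new accrual as 33 or 30, so that 36 is reached either way.

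Which way to resolve it is for the sponsor; no dose or cohort rule is proposed here. The cost is protocol wording. The total of 36 does not change, because patients treated at the recommended dose count towards it, and the overall 48 is not exceeded.

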9.3. Phase II

The primary endpoint for phase II portion is the decrease of transcript levels by at least one log (or undetectable transcript level) within 12 months. Including the 6 patients treated at the recommended phase II dose level in the phase I part, a total of 36 patients will be accrued.

9.3.1. **Efficacy Monitoring**

Since the efficacy of the drug will be assessed over a long period of time (12 months) and the accrual rate is relatively fast (1-2 patients per month), no formal futility monitoring rule will be applied. However, the PI and the study committee will meet regularly, and the study will be stopped early if consensus has been reached on any clear indications of poor efficacy of the drug.

9.3.2. **Toxicity Monitoring**

The method of Thall, Simon, and Estey will be used to perform interim safety monitoring [1]. The safety monitoring of the trial will be initiated after the first 6 patients have been evaluated, and then monitored continuously. The monitoring rule for toxicity is $P(\theta_E > 0.20 | \text{data}) > 0.90$, where θ_E is the proportion of any DLT (as defined in section 4.3.3), and is assumed to follow a non-informative prior of Beta (0.4, 1.6). Namely, the trial will be terminated if at any time during the study there is a more than 90% chance that the average rate of DLT is more than 20%. The stopping boundaries of the trial are ≥ 3 out of 6, ≥ 4 out of 7, ≥ 5 out of 10, ≥ 6 out of 14, ≥ 7 out of 18, ≥ 8 out of 22, ≥ 9 out of 26, ≥ 10 out of 30, ≥ 11 out of 34 patients experienced DLT.

Table 2: Operating characteristics of Safety Monitoring (based on 10000 simulations)				
True Probability	Stop Probability	Trial Sample Size Percentile		
		25%	50%	75%
0.10	0.02	36	36	36
0.20	0.25	36	36	36
0.30	0.69	6	17	36
0.40	0.96	6	8	16

All calculations were performed using Multc99.

9.4. **Statistical Methods**

Data analysis will be performed using SAS or S-plus, whichever is appropriate. All patients who receive at least one dose of therapy will be included in the primary efficacy and toxicity analysis. Patients who do not have molecular response and

withdraw within 12-months after initiation of treatment will be counted as failure in the primary efficacy analysis.

The rate of molecular response will be estimated with 95% confidence interval. The null hypothesis is that the response rate is 5%, and alternative hypothesis is that the response rate is 20%. If a 20% response is reached, the study would be considered positive. Under this setting, 36 patients can provide a power of 87% for a one-sided test of the above hypothesis at significance level $\alpha=5\%$.

10. Protocol Amendments, Deviations and Regulatory

Any amendment to this protocol must be agreed to by the Principal Investigator and by MD Anderson Cancer Center and by Celgene. Amendments should only be submitted to IRB after consideration of M. D. Anderson Cancer Center, Celgene review. Written verification of IRB approval will be obtained before any amendment is implemented.

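### The success rule in Section 9.4 (20% response reached) is not the test that gives 87% power; read literally it has 43% power at the planned alternative

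*Combined protocol and SAP*

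**What the plan says.** Section 9.3 makes the phase II primary endpoint binary: a fall of at least one log in transcript level, or undetectable transcripts, within 12 months. Counting the 6 phase I patients treated at the recommended dose, "a total of 36 patients will be accrued".

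Section 9.4 sets the null response rate at 5% and the alternative at 20%. It then says: "If a 20% response is reached, the study would be considered positive". The next sentence gives the power: "Under this setting, 36 patients can provide a power of 87% for a one-sided test of the above hypothesis", at a 5% significance level. The same paragraph says: "The rate of molecular response will be estimated with 95% confidence interval".

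No rejection boundary in number of responders appears anywhere in Section 9. The 20% sentence is the only statement of what makes the study positive.

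**The concern.** The 20% figure does two jobs: it is the true rate at which power is calculated, and it is the result that must be reached for success. A test designed to detect a true rate of 20% against 5% rejects at an observed rate well below 20%. If the observed rate must itself reach the alternative, power at that alternative will be around one half, whatever the sample size.

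This is the deciding criterion for the phase II primary endpoint of a single-arm trial. With 5, 6 or 7 responders, one sentence of Section 9.4 supports calling the trial a success and another supports calling it a failure. As the plan stands, that choice would be made after the data are seen. The 87% also tells readers that the design is much more likely to recognise an active combination than the written rule allows.

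**Working it through.** **Inputs.** From Section 9.4: p0 = 0.05, p1 = 0.20, one-sided alpha = 0.05. From Sections 9.3 and 9.4: n = 36. A single-stage calculation with a fixed denominator is appropriate, because Section 9.3.1 applies no formal futility rule and Section 9.4 counts non-responders who withdraw within 12 months as failures.

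**Formula.** If the study is called positive at r or more responders, then

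P(X ≥ r | p) = Σ from k = r to 36 of C(36, k) p^k (1 − p)^(36 − k).

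At p = 0.05 this is the type I error; at p = 0.20 it is the power.

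| Positive if at least | Observed rate | Type I error (p = 0.05) | Power (p = 0.20) |
|---|---|---|---|
| 4 | 11.1% | 0.1037 | 0.948 |
| **5** | **13.9%** | **0.0324** | **0.873** |
| 6 | 16.7% | 0.0083 | 0.754 |
| 7 | 19.4% | 0.0018 | 0.599 |
| **8** | **22.2%** | **0.0003** | **0.434** |
| 9 | 25.0% | 0.0001 | 0.284 |

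**Step 1: reproduce the plan's figure.** A cut-off of 4 exceeds the 5% level (0.1037). A cut-off of 5 is the smallest that meets it, and its power is 0.873. That is the stated 87%, so the power figure is correct for the exact one-sided test. The one-sided approximations fit less well: 88.7% for the arcsine and 91.2% for the normal.

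**Step 2: apply the written success rule.** 0.20 × 36 = 7.2, so the first count to reach 20% is 8. Power is 0.434. A combination with exactly the targeted activity would be declared not positive with probability 1 − 0.434 = 0.566.

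**Step 3: how often the two rules conflict.** They differ at 5, 6 and 7 responders.

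- True rate 20%: 0.873 − 0.434 = 0.439.
- True rate 5%: 0.0324 − 0.0003 = 0.032.

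**Step 4: a lenient reading.** If 7/36 (19.4%) is accepted as about 20%, power is 0.599. The conflict is then confined to 5 or 6 responders, with probability 0.873 − 0.599 = 0.274 at a true rate of 20%.

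**Step 5: what true rate the literal rule needs.** For 8 or more of 36, power is 0.710 at a true rate of 25%, 0.830 at 28% and 0.888 at 30%. The rule therefore reaches 87% only between 28% and 30%, a rate the plan does not posit.

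**Side check on the interval.** At 5/36 the exact (Clopper-Pearson) two-sided 95% interval is 4.7% to 29.5%. It includes the 5% null although the one-sided test rejects. This happens only at 5 responders (probability 0.119 at a true rate of 20%); at 6/36 the lower limit is 6.4%. The lower limit of the 90% interval at 5/36 is 5.6%, which agrees with the test.

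**The case against.** The strongest reply is that the 20% sentence loosely restates the target and that the one-sided 5% test is the real decision rule. The 87% is then right and only the wording is unclear. This does not rescue the text. The alternative has already been given in the sentence before, and this sentence attaches a study conclusion to a response that is reached, which data can do and a true rate cannot. Even on this reading the plan has no stated cut-off and still needs one.

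Four further points deserve weight.

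- **The bar may be deliberate.** A clinical bar above the statistical one is legitimate and errs on the conservative side, since its type I error is 0.0003. But its power is then 43%, and the plan should say so.
- **Rounding matters to one consequence.** That a truly active combination would more often than not be called a failure holds at 8 of 36 (56.6%). It does not hold if 7 of 36 is accepted (40.1%). The mismatch with 87% remains in both cases.
- **The denominator could differ from 36.** Section 9.4 analyses every patient who receives a dose, and the trial may stop early. A fixed cut-off of 5 would have type I error 0.057 at n = 42 and 0.091 at n = 48. The planned phase II number is 36, so the finding is unaffected, but the repaired text should cover this case.
- **The confidence interval is planned for estimation.** Nothing makes it a decision rule, and a two-sided 95% interval beside a one-sided 5% test is common. The boundary disagreement is real, but changing the interval is optional.

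**Conclusion.** The concern holds. The 87% is arithmetically correct, but it belongs to a rule of 5 or more responders of 36, which the plan never states. The rule it does state needs 8 or more, with power 0.434 and type I error 0.0003. At the planned alternative the two rules give opposite conclusions with probability 0.439.

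These figures assume 36 analysed patients, exact binomial calculation, no interim efficacy rule, and the literal reading that an observed rate of at least 20% is required. On the lenient reading (7 of 36) power is 0.599 and the conflict probability 0.274, so the conclusion stands. The confidence interval point is secondary and the conclusion does not depend on it.

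**What to change.** Replace the success sentence in Section 9.4 with one rule expressed as a responder count. There are two coherent choices:

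1. **Keep the test.** The study is positive if 5 or more of 36 patients respond (exact one-sided type I error 0.032, power 0.873 at a true rate of 20%). This preserves the sample size and the stated power.
2. **Keep the 20% bar.** The study is positive if 8 or more of 36 patients respond (type I error 0.0003, power 0.434 at a true rate of 20%). The 87% claim must then be removed, and the sponsor should decide whether 43% power is acceptable.

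Under the first choice, add that if the number analysed is not 36, the exact one-sided 5% test is applied to the actual number. Optionally, report a two-sided 90% exact interval or a one-sided 95% lower bound beside the test, or state that the 95% interval is for estimation only.

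The cost is one or two sentences in Section 9.4, settled before outcome data are reviewed. No extra patients or assessments are needed.
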